## 8 PROHIBITED AND RESTRICTED MEDICATIONS AND PROCEDURES

Medications (including vitamins and over-the-counter [OTC] medications and therapies) used within 90 days before the screening visit (visit 1) will be recorded in the eCRF. The administration of any additional medication during the study (including OTC medications and vitamins) beyond those specified in the protocol will be clearly documented both in the source document and the eCRF.

No medication, other than the study medication and allowed medications, should be taken during the study. Exceptions to this rule apply to medication that may be needed to treat AEs. Such administration will be clearly documented and cross-referenced with the AE on the eCRF. If administration of any prohibited medication becomes necessary during the study for medical reasons, the Investigator should consult with the Sponsor to determine whether to continue or withdraw the patient from further participation in the study.

All other therapies prohibited as per protocol must have been discontinued prior to the protocol specified periods. Patients are not allowed to enter the study if they receive any prohibited concomitant medication or medication in a dosage not allowed and which cannot be discontinued or reduced. These medications should only be discontinued if the Investigator decides that discontinuing patients from therapy is the best course of action for the patient. These prohibited medications and therapies should not be discontinued for the sole purpose of making a patient eligible for enrollment into the study.

### 8.1 PROHIBITED CONCOMITANT MEDICATIONS

The medications listed in [Table 8-1](#) are not allowed or are restricted during this study (Part 1 and Part 2).

**Table 8-1. Prohibited Medications (Part 1 and Part 2)**

Type of medication	Washout period before the screening visit (visit 1) and throughout the study (unless otherwise specified)
Prohibited	
Depot steroids	90 days
Immunologically active biologic medications (eg, anti-tumor necrosis factor alpha, abatacept)	90 days
Any other investigational drugs	30 days or 5 half-lives, whichever comes first
Strong CYP3A4 inhibitors (eg, azole antifungals, ritonavir, clarithromycin)	30 days
Immunosuppressive therapy (eg, methotrexate, gold, azathioprine)	30 days
Marijuana (via smoking)	30 days
Oral or systemic corticosteroids	30 days

Type of medication	Washout period before the screening visit (visit 1) and throughout the study (unless otherwise specified)
ICS (monotherapy) or ICS/LABA combination therapy	30 days
LAMA or LAMA/LABA combination therapy	21 days
Beta-adrenergic receptor blocking agents a	14 days
Cromones	14 days
Leukotriene modifiers	14 days
Monoamine oxidase inhibitors	14 days
Polycyclic antidepressants	14 days
Once or twice daily LABA monotherapy (eg, indacaterol)	7 days
Oral $\beta$ 2-agonists (tablets, syrup)	48 hours for long and 12 hours for short
H 2 antagonists (eg, cimetidine)	24 hours
Drugs of abuse (cannabinoids, amphetamines, barbiturates, cocaine, benzodiazepines, methadone, and opiates) b	A negative test is required at the screening visit and use is prohibited throughout the study.

- a. Cardioselective beta blockers are permitted as long as therapy was initiated at least 7 days before the screening visit (visit 1) and is expected to remain at a stable dose throughout the study.
- b. If a patient has a positive urine drug screen for a class of drug which is consistent with a medication that the patient is currently prescribed (excluding inhaled marijuana), the patient can be considered eligible for the study after the prescription is confirmed by the Investigator. Inhaled marijuana is not permitted even if prescribed.

CYP=cytochrome P450; ICS=inhaled corticosteroid; LAMA=long-acting anti-muscarinic agent; LABA=long-acting  $\beta$ 2 agonist.

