10. Patient is a current smoker or non-smoker with a minimum 10 pack-years of historical use (the equivalent of one pack per day for 10 years).
11. Patient is able to withhold all inhaled SABAs for at least 6 hours and SAMAs for at least 8 hours prior to lung function assessments on study visit days.
12. Patient is medically able to tolerate permitted medications without a significant adjustment of dosage, formulation, dosing interval for the duration of the study, and judged able by the Investigator to withhold them for the specified minimum time intervals prior to each clinic visit.
13. Patient is free of any concomitant conditions or treatments that could interfere with study conduct, influence the interpretation of study observations/results, or put the patient at increased risk during the study (eg, patient is not able to self-administer study medication or self-complete the diary).
14. Patient did not experience an AE that in the opinion of the Investigator would result in failure to meet the inclusion/exclusion criteria during the screening period.
15. If female, is currently not pregnant, breast feeding, or attempting to become pregnant (for 4 weeks before the screening visit (visit 1) and throughout the duration of the study), and is of
  - nonchildbearing potential, defined as:
    - $\geq 1$  year post-menopausal
    - surgically sterile (tubal ligation, oophorectomy, or hysterectomy)
    - diagnosed as infertile and not undergoing treatment to reverse infertility
  - or is of
    - childbearing potential, has a negative serum pregnancy test at the screening visit (visit 1), and willing to commit to using a consistent and acceptable method of birth control as defined below for the duration of the study or exclusively has same-sex partners:
      - systemic contraception used for  $\geq 1$  month prior to screening, including birth control pills, transdermal patch (EVRA® or equivalent), vaginal ring (NUVARING® or equivalent), levonorgestrel implant (NORPLANT® or equivalent), or injectable progesterone (DEPO-PROVERA® or equivalent)
      - double barrier methods (condoms, cervical cap, diaphragm, and vaginal contraceptive film with spermicide)

- intrauterine device (IUD) with a low failure rate <1% per year
- monogamous with a vasectomized male partner or exclusively has same-sex partners

or is of

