## 6.2 EXCLUSION CRITERIA

A patient who meets any of the following exclusion criteria must not be enrolled:

1. Known respiratory disorder other than COPD, including but not limited to the following: alpha-1-antitrypsin deficiency, cystic fibrosis, significant asthma, active bronchiectasis, sarcoidosis, lung fibrosis, pulmonary hypertension, pulmonary edema, or interstitial lung disease.
2. Evidence or history of other clinically significant disease or abnormality (such as congestive heart failure, uncontrolled hypertension, uncontrolled coronary artery disease, myocardial infarction, stroke, glaucoma or cardiac dysrhythmia), sleep apnea, malignancy (excluding basal cell carcinoma). In addition, historical or current evidence of significant hematologic, hepatic, neurologic, psychiatric, renal, pulmonary, or other diseases that in the opinion of the Investigator, would put the patient at risk through study participation, or would affect the study analyses if the disease exacerbated during the study.
3. Known active tuberculosis.
4. Hospitalization for a COPD exacerbation or pneumonia within 12 weeks prior to the screening visit (visit 1).
5. History of frequent COPD exacerbations of moderate to severe severity averaging 2 or more per year, or 2 or more exacerbations per year which resulted in hospitalization, averaged over the last 3 years.
6. Treatment for a non-hospitalized COPD exacerbation or pneumonia requiring antibiotics and/or systemic corticosteroids within 12 weeks prior to the screening visit (visit 1).
7. History of paradoxical bronchospasm, narrow angle glaucoma, prostatic hypertrophy or bladder neck obstruction, which, in the Investigator's opinion, would contraindicate the use of an anticholinergic agent.
8. The patient is pregnant or lactating, or plans to become pregnant or donate gametes (ova or sperm) during the study period or for 30 days after the patient's

- last study-related visit (for eligible patients only, if applicable). Eligible female and male patients unwilling to employ appropriate contraceptive measures to ensure that pregnancy will not occur during the study will be excluded. Any patient becoming pregnant during the study will be withdrawn from the study.
9. Treatment with any protocol prohibited medications during the prescribed washout period before the screening visit (visit 1).
  10. Inability to discontinue COPD medications during the screening, run-in, and treatment periods.

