- 11) Vital signs will be collected within 60 minutes of measuring the predose FEV1 on days 0, 21, and 42.
- 12) Single blind run-in must be dispensed 14 to 16 days prior to randomization. Patients will administer the single-blind placebo LUPINHALER one daily in the morning for 14 (+2) days after completing the FEV1 measurements.
- 13) Patient has demonstrated ≥15% reversibility of FEV1 within 30 or 60 minutes following 68 mcg of ipratropium bromide inhalation (pMDI). If required, spacers are permitted for use during reversibility testing for ipratropium bromide administration. Patients who do not demonstrate a positive improvement of at least 15% in FEV1 measured at 30 or 60 minutes (±5 minutes) post inhalation will not be eligible to participate in the study. However, based on Investigator judgment, patients will be allowed to retest once no sooner than 24 hours and no later than 2 weeks after initial failure to meet the reversibility criteria. Reversibility values of 14.50-14.99 will be rounded to 15.
- 14) A stability limit will be established at the screening visit (visit 1) to determine alert criteria for worsening COPD during the screening and run-in periods, and will be calculated by selecting the best pre-bronchodilator qualifying FEV1 measurement at the screening visit using the onsite spirometer x 80%.

- 15) Two stability limits (at home and investigational center) will be re-established at the randomization visit (visit 2) for use during the double-blind and open-label treatment periods. The at home limit will be calculated by taking the mean of the best predose FEV1 measurements on the last 3 days before randomization on the electronic flow meter (home device) x 80%, and the investigational center limit will be the mean FEV1 of the predose pre-bronchodilator qualifying FEV1 measurements (-30 and -15 minutes) using the onsite spirometer x 80%.
- 16) A subset of patients (approximately 120 patients) at select investigational centers who successfully completed Part 1 will be eligible for enrollment into the open-label extension (Part 2).

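### Table 8-1 takes the shorter of two washout limits for other investigational drugs, so a drug outside the 90-day biologics row with a half-life above 6 days may not have had 5 half-lives by visit 1

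*Protocol*

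**What the plan says.** In protocol Table 8-1 (Section 8.1), the row "Any other investigational drugs" carries the limit "30 days or 5 half-lives, whichever comes first". The column heading is "Washout period before the screening visit (visit 1) and throughout the study (unless otherwise specified", so the limit is counted back from visit 1.

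The row becomes an eligibility rule through exclusion 9 (Section 6.2), which excludes "Treatment with any protocol prohibited medications during the prescribed washout period before the screening visit (visit 1". No other exclusion criterion deals with recent use of an investigational drug, and the SAP gives no different limit.

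Two other provisions bear on the point. Table 8-1 has a separate 90-day row for "Immunologically active biologic medications (eg, anti-tumor necrosis factor alpha, abatacept" and similar products. Inclusion 13 (Section 6.1) contains a general condition: "Patient is free of any concomitant conditions or treatments that could interfere with study conduct, influence the interpretation of study observations/results". It states no time limit.

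**The concern.** When a washout is expressed both in days and in half-lives, the half-life part is there for drugs that leave the body slowly. Joined as they are in this row, the two limits work the other way. The half-life part acts only when it is shorter than 30 days, and has no effect on a slowly cleared drug.

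A patient admitted under the row is compliant. No prohibited-medication deviation arises from it under the categories in SAP Section 13.2, so nothing in the row would remove the patient from the per-protocol set that decides bioequivalence. What is at stake is eligibility and safety: a patient could take the ipratropium reversibility test, and then study drug, with a material amount of a poorly characterised product still present.

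The table also does not say whether an investigational product belonging to a listed class, for example a LAMA, must meet that class's row as well.

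**Working it through.** The plan gives no figure to reproduce here, so the check is of the rule itself.

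**Inputs**
- Washout before visit 1, read literally: the smaller of 30 days and 5 × h, where h is the half-life in days (Table 8-1).
- Time from visit 1 to first randomized dose: 14 to 16 days. Table 9-1, footnote 12, says "Single blind run-in must be dispensed 14 to 16 days prior to randomization", and Section 9.3.1 places visit 1 immediately before the run-in. I take the two as the same day; a longer visit 1 would add time.
- Half-life of the earlier investigational drug: not in the documents. I assume a range up to 30 days.
- First-order elimination (assumed): fraction remaining = 0.5^(days since last dose / h).

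**Where the limits cross**
- At visit 1: 5 × h = 30, so h = 30/5 = 6 days.
- At first dose: 30 + 14 = 44 days have passed, or 30 + 16 = 46. Five half-lives are still incomplete when h exceeds 44/5 = 8.8 days, or 46/5 = 9.2 days.

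**Half-life of 6 days or less.** The wait is 5 × h, so the fraction left at visit 1 is 0.5^5 = 3.1%. The run-in reduces it further; at h = 6 it is 0.5^(44/6) = 0.6% at first dose. There is no clearance gap.

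**Half-life above 6 days.** The wait is 30 days:

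| Assumed half-life (days) | 5 half-lives (days) | Left at visit 1, 0.5^(30/h) | Left at first dose, 0.5^(44/h) |
|---|---|---|---|
| 7 | 35 | 5.1% | 1.3% |
| 10 | 50 | 12.5% | 4.7% |
| 14 | 70 | 22.6% | 11.3% |
| 20 | 100 | 35.4% | 21.8% |
| 30 | 150 | 50.0% | 36.2% |

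With a 16-day run-in, the first-dose figures for 14 and 20 days become 10.3% and 20.3%.

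**Effect of the biologics row.** A product covered by the 90-day row would leave 0.5^(90/14) = 1.2% at visit 1 for a 14-day half-life and 0.5^(90/20) = 4.4% for a 20-day half-life. The table above therefore applies only to products outside that row.

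**The case against.** The strongest case against is that the gap is narrow and nothing measurable follows from it.

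- **Half-life.** For half-lives up to 6 days the rule delivers 5 half-lives, and nobody is randomized until at least 14 days later. This stands. A reader might infer that a short-lived product admitted after hours or days is a further failing, but by the row's own half-life standard such a drug has cleared.
- **Other rows.** Immunologically active biologics have 90 days. The remaining rows are by type of medication and are not limited to marketed products, so an investigational LAMA or depot steroid may already fall under its class row. The biologics part stands. The class part is a reasonable reading, but the table does not state it.
- **Comparison within the table.** A reader might infer that the row contradicts its neighbours because several have fixed waits of 21, 30 or 90 days. The same table also has 7 days for LABA monotherapy, 48 and 12 hours for oral beta-2 agonists and 24 hours for H2 antagonists. Short waits are not out of place, and there is no internal contradiction.
- **Safeguards.** Inclusion 13 lets the investigator refuse a patient, and Section 8 has medications from the 90 days before visit 1 recorded. Both help, but neither sets a limit for a slowly cleared drug.
- **Primary endpoint.** A reader might infer that a fading residual effect would add noise to the AUC or bias the comparison of test with reference. The documents do not support going that far. Each visit's AUC uses that visit's own predose baseline (SAP 9.2), the model has a period term (SAP 13.6.1), the six sequences are balanced, and continuation criterion 4 checks predose FEV1 at visits 3 and 4 against visit 2. Nothing links residual concentration to residual FEV1 effect.

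**Conclusion.** The point holds in a limited form. As printed, the half-life limit can only shorten the wait. For an investigational drug outside the biologics row with a half-life above 6 days, a patient can pass exclusion 9 before 5 half-lives have elapsed. Judged at the first randomized dose, the threshold is about 8.8 to 9.2 days.

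The size rests on a literal reading of the row, first-order elimination and assumed half-lives. The documents name no particular drug and do not say how many candidates would be affected; the number is probably small. No sample size, power or alpha figure changes, an effect on FEV1 cannot be quantified, and bias between test and reference is unlikely. This is a minor flaw in an eligibility rule, worth correcting because the correction is nearly free.

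**What to change.** Correct the closing phrase of the row in Table 8-1 so that the half-life limit can extend the wait for a slowly cleared drug and not only shorten it. The sponsor should confirm which limit is meant to govern and set the duration; no washout length is proposed here.

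Add a sentence saying whether an investigational product must also meet the Table 8-1 row for its own drug class.

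Exclusion 9 refers to the prescribed washout, so it needs no rewording, and neither does the SAP. The cost is a phrase and a sentence in one table, and a few candidates who wait longer or are not eligible. Because prior medications are already recorded for 90 days before visit 1, enrolled patients with investigational-drug use in that window can be identified without new data collection.

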### 8.1.1 Washout Restrictions during Part 1 of the Study Only

The washout period for LAMA or LABA is as follows:

- LAMA medications (including mono products and combination products containing LAMAs [eg, LAMA/LABA]) will not be permitted within 21 days of the screening visit (visit 1) and throughout the study (except for the study medication provided at each treatment period). Any patients taking LAMA medications will need to discontinue these medications, and at the Investigator's discretion, the LAMA may be replaced with ipratropium bromide (SAMA), adhering to the washout restrictions below.
- LABA mono products will need to be discontinued 7 days before the screening visit (visit 1) and throughout the study. Any patients taking LABAs will need to discontinue these medications, and at the discretion of the Investigator, the LABA may be replaced with ipratropium bromide (SAMA), adhering to the washout restrictions below.
- ICS/LABA combination products will need to be discontinued 30 days before the screening visit (visit 1) and throughout the study. Any patients taking

ICS/LABAs will need to discontinue these medications, and at the discretion of the Investigator, the ICS/LABA may be replaced with ipratropium bromide (SAMA), adhering to the washout restrictions below

Patients should refrain from taking the following medications from the specified time points below prior to spirometry assessments at each clinic visit (both days of each inpatient visit) during Part 1 of the study:

- SABAs 6 hours
- SAMAs: 8 hours
- short-acting forms of theophylline: 12 hours
- twice-a-day controlled-release forms of theophylline: 24 hours
- once-a-day controlled-release forms of theophylline: 36 hours
- caffeine-containing medications (eg, MIDOL®, EXCEDRIN®) 6 hours

If a patient requires the use of a SABA for rescue during the serial spirometry, the administration of the rescue medication should be recorded as a protocol deviation and the patient should continue with the pulmonary function testing as scheduled for that day.

### 8.1.2 Permitted Medication with Restrictions during Part 1 of the Study Only

The following medications ([Table 8-2](#)) are also permitted during the study if the noted conditions are met. Note: If patients are taking these restricted medications on an as needed (PRN) basis, then a start/stop date must be entered in the eCRF prior to the screening visit (visit 1) and for each instance thereafter, as applicable.

**Table 8-2. Permitted Medications with Restrictions**

Type of medication	Washout period before the screening visit (visit 1), unless otherwise specified
Nasal corticosteroids	Chronic stable doses at least 14 days duration before the screening visit (visit 1) and stable throughout the study duration allowed throughout the study
Theophyllines	Permitted if without a significant adjustment of dosage, formulation, dosing interval for the duration of the study, and judged able by the Investigator to withhold them for the time intervals prior to each clinic visit -short-acting forms: 12 hrs -twice a day controlled-release forms: 24 hrs -once a day controlled-release forms: 36 hrs.
PDE4 inhibitors	Permitted if without a significant adjustment of dosage, formulation, and dosing interval for the duration of the study
Oral or nasal antihistamines (eg, loratadine, diphenhydramine, cetirizine)	Discontinue 24 hours before each visit and may resume after the visit

### 8.1.3 Permitted Concomitant Medication/Therapy during Part 2 of the Study Only

In Part 2 of the study, patients will be supplied with Lupin Tiotropium Bromide Inhalation Powder for once daily administration over 72 days.

Patients will also be permitted to resume other non-study medications and albuterol/salbutamol MDI as long as the medications do not contravene the prohibited medications in [Table 8-1](#), excluding the use of the LAMA study medication.

## 8.2 GENERAL AND DIETARY RESTRICTIONS

For Part 1, patients will be required to comply with the following restricted activities:

- Patients are not to engage in strenuous exercise on the mornings of any scheduled visit (visit 1 through visit 4).
- If possible, patients should avoid cold air exposure on the mornings prior to spirometry testing at any scheduled visit (visit 1 through visit 4). Patients who experience bronchial symptoms related to exposure to cold air should be adequately stabilized at room temperature before any study-related pulmonary function tests (PFTs) are conducted.
- Patients should not smoke or be in a smoky atmosphere for at least 1 hour prior to spirometry assessments at any scheduled visit (visit 1 through visit 4).
- Patients should avoid intake of caffeinated beverages for at least 6 hours prior to spirometry testing on the mornings of any scheduled visit (visit 1 through visit 4).

Note: If the patient has failed to comply with any of the general and dietary restrictions above, the visit/spirometry should be postponed until the condition is met (see [section 9.3.6](#)).

For Part 2, there are no activity or dietary restrictions.

## 9 STUDY PROCEDURES

### 9.1 SCHEDULE OF EVENTS

The schedule of events is provided in [Table 9-1](#).

**Table 9-1. Schedule of Events**

Study visit	Screening period	Single-blind run-in period	Part 1 Double-blind treatment period							Part 2 Open-label extension						ET 	
	Visit 1		NA	TP1 (Visit 2)		TP2 (Visit 3)		TP3 (Visit 4)		F/U 	Visit 5	Visit 6	Visit 7	Visit 8	Visit 9		Visit 10
Study days 	-44 to -14 	14-16 day period before day 0	0	1	21 (+3)	22	42 (+3)	43	50 (±3)	43 	57 (±2)	71 (±2)	85 (±2)	99 (±2)	115 (+3)	122 (±3)	NA
Clinic visit 	X		X	X	X	X	X	X	Tele- phone only	X	Tele- phone only	X	Tele- phone only	X	X	Tele- phone only	X
Informed consent	X																
Assign patient via IRT	X																
Assess inclusion/ exclusion criteria	X																
Demography	X																
Physical examination	X 							X							X		X
Height and weight	X																
HEENT and chest examination			X		X		X					X		X			
Medical history including prior concomitant medications	X																
12-lead ECG	X		X		X		X					X		X	X		
Clinical laboratory tests (hematology, biochemistry, and urinalysis)	X																
Serum pregnancy test (female patients of	X							X 							X 		X

Study visit	Screening period	Single-blind run-in period	Part 1 Double-blind treatment period							Part 2 Open-label extension							ET 
	Visit 1		NA	TP1 (Visit 2)		TP2 (Visit 3)		TP3 (Visit 4)		F/U 	Visit 5	Visit 6	Visit 7	Visit 8	Visit 9	Visit 10	
Study days 	-44 to -14 	14-16 day period before day 0	0	1	21 (+3)	22	42 (+3)	43	50 (±3)	43 	57 (±2)	71 (±2)	85 (±2)	99 (±2)	115 (+3)	122 (±3)	NA
Clinic visit 	X		X	X	X	X	X	X	Tele- phone only	X	Tele- phone only	X	Tele- phone only	X	X	Tele- phone only	X
childbearing potential only)																	
Urine pregnancy test (female patients of childbearing potential only)			X														
Urine drug screen	X																
Vital signs measurements 	X		X 	X	X 	X	X 	X				X		X	X		X
Demonstrate study medication inhalation technique	X		X		X		X			X		X		X			
Demonstrate albuterol/salbutamol MDI inhalation technique	X		X		X		X			X		X		X			
Dispense single-blind run-in medication		X 															
Assess inspiratory flow rate via In-Check DIAL device	X		X		X		X										
Ipratropium reversibility 	X																
Study qualifying FEV 1	X																
Determine FEV 1 baseline/stability limits	X 		X 														
Administer single-blind run-in medication		X															

Study visit	Screening period	Single-blind run-in period	Part 1 Double-blind treatment period							Part 2 Open-label extension							ET 
	Visit 1		NA	TP1 (Visit 2)		TP2 (Visit 3)		TP3 (Visit 4)		F/U 	Visit 5	Visit 6	Visit 7	Visit 8	Visit 9	Visit 10	
Study days 	-44 to -14 	14-16 day period before day 0	0	1	21 (+3)	22	42 (+3)	43	50 (±3)	43 	57 (±2)	71 (±2)	85 (±2)	99 (±2)	115 (+3)	122 (±3)	NA
Clinic visit 	X		X	X	X	X	X	X	Tele- phone only	X	Tele- phone only	X	Tele- phone only	X	X	Tele- phone only	X
Collect single-blind run-in medication			X														X
Review randomization criteria			X														
Randomization via IRT			X														
Review continuation criteria					X		X			X	X	X	X	X			
Administer study medication at clinic			X		X		X			X							
Enroll in open-label extension via IRT 										X							
Predose and serial FEV 1 measurements 			X	X	X	X	X	X									
Dispense ed diary/ electronic flow meter	X 									X							
Review ed diary/ electronic flow meter instructions	X		X		X		X			X							
Dispense albuterol/salbutamol MDI, as applicable	X 	X	X		X		X			X		X		X			
Dispense/collect placebo trainer	X		X		X		X										
Dispense study medication 			X		X		X			X							
Assess ed diary data	X		X		X		X	X			X	X	X	X	X		X
Collect ed diary/	X		X					X							X		X

Study visit	Screening period	Single-blind run-in period	Part 1 Double-blind treatment period							Part 2 Open-label extension							ET 
	Visit 1		NA	TP1 (Visit 2)		TP2 (Visit 3)		TP3 (Visit 4)		F/U 	Visit 5	Visit 6	Visit 7	Visit 8	Visit 9	Visit 10	
Study days 	-44 to -14 	14-16 day period before day 0	0	1	21 (+3)	22	42 (+3)	43	50 (±3)	43 	57 (±2)	71 (±2)	85 (±2)	99 (±2)	115 (+3)	122 (±3)	NA
Clinic visit 	X		X	X	X	X	X	X	Tele- phone only	X	Tele- phone only	X	Tele- phone only	X	X	Tele- phone only	X
electronic flow meter, as applicable																	
Check for issues with study inhalers		X	X		X		X			X	X	X	X	X	X		X 
Collect COPD exacerbation data	X	X	X	X	X	X	X	X	X	X	X	X	X	X	X	X	X
Record AEs	X	X	X	X	X	X	X	X	X	X	X	X	X	X	X	X	X
Record concomitant medication/therapies	X	X	X	X	X	X	X	X	X	X	X	X	X	X	X	X	X
Collect study medication			X		X		X								X		X
Collect albuterol/salbutamol MDI, as applicable	X		X		X		X	X				X		X	X		X
Schedule next visit	X			X		X		X		X	X	X	X	X	X		
Discuss COPD treatment options	X							X	X						X	X	X
Discharge patient via IRT									X							X	X
Home-based FEV 1 measurements	Record morning predose in ed diary/electronic flow meter 									Record morning predose and 2 hours postdose in ed diary/electronic flow meter							
Assess EXACT symptom scores	Record once daily in the evening before bedtime via ed diary									Record once daily in evening before bedtime via ed diary							
Albuterol/salbutamol MDI medication use	Record daily in ed diary									Record daily in ed diary							

1) For patients participating in Part 1 only, a follow-up visit will occur via phone contact by investigational center personnel 7 days (±3 days) after completing visit 4.

- 2) This follow-up visit will only be required for patients participating in Part 2 of the study, and will occur via phone contact by investigational center personnel 7 ±3days after the final treatment visit (visit 10).
- 3) Regardless if patient is participating in Part 1 or Part 2, the assessments listed for ET will be performed for any patient who is withdrawn prematurely from the study.
- 4) As there is only the potential to extend visit intervals with permitted visit windows, the terminology of study days will not necessarily represent the exact day of the visit.
- 5) The screening visit (visit 1) may take place over several days beginning on day -44 to -14 dependent on the patient's washout. If a patient is washing out of ICS (monotherapy) or ICS/LABA combination therapy, an additional 3 days is permitted to complete the assessments for the screening visit (visit 1). All results, with the exception of the clinical laboratory assessments, must be available and evaluated prior to commencing the run-in period. The clinical laboratory results must be available and evaluated prior to randomization. The procedures for the screening visit (visit 1), with the exception of signing of the ICF, performing a pre-washout physical examination, and dispensing/completing the diary, cannot occur until appropriate medication washouts have been completed in accordance with the protocol. Once the washout requirements have been met, the screening visit (visit 1) should immediately precede the start of the run-in period. If a patient does not require washout, and the patient passes all entry criteria at the screening visit (visit 1), the patient will be eligible to enter the run-in period on the same day as the screening visit (visit 1). The patient must successfully complete the visit 1 procedures/assessments prior to entering the run-in period.
- 6) After completion of visit 4 (days 42 and 43), patients will either be discharged from the study after completing all double-blind study assessments at visit 4 or a subset of patients (approximately 120 patients) will be eligible for enrollment into a 12-week open-label extension, which will begin on the same day as the final visit in the double blind treatment period.
- 7) All visits for Part 1 should be scheduled in the mornings between 0600 and 1000 and spirometry testing should begin at ±1 hour of the start of visit 1 testing time.
- 8) If washout of baseline therapy is needed, then 2 physical examinations are required: one before a patient commences the washout period and one after the washout period ends, prior to enrolling into the run-in period.
- 9) The visit 4 end of study serum pregnancy test will be performed for women of childbearing potential who are only participating in Part 1 of the study. For women of childbearing potential who are participating in both Part 1 and Part 2, the end of study serum pregnancy test will be performed at visit 10.
- 10) Vital signs measurements include blood pressure, heart rate, respiration rate, and temperature.
- 11) Vital signs will be collected within 60 minutes of measuring the predose FEV1 on days 0, 21, and 42.
- 12) Single blind run-in must be dispensed 14 to 16 days prior to randomization. Patients will administer the single-blind placebo LUPINHALER one daily in the morning for 14 (+2) days after completing the FEV1 measurements.
- 13) Patient has demonstrated ≥15% reversibility of FEV1 within 30 or 60 minutes following 68 mcg of ipratropium bromide inhalation (pMDI). If required, spacers are permitted for use during reversibility testing for ipratropium bromide administration. Patients who do not demonstrate a positive improvement of at least 15% in FEV1 measured at 30 or 60 minutes (±5 minutes) post inhalation will not be eligible to participate in the study. However, based on Investigator judgment, patients will be allowed to retest once no sooner than 24 hours and no later than 2 weeks after initial failure to meet the reversibility criteria. Reversibility values of 14.50-14.99 will be rounded to 15.
- 14) A stability limit will be established at the screening visit (visit 1) to determine alert criteria for worsening COPD during the screening and run-in periods, and will be calculated by selecting the best pre-bronchodilator qualifying FEV1 measurement at the screening visit using the onsite spirometer x 80%.

- 15) Two stability limits (at home and investigational center) will be re-established at the randomization visit (visit 2) for use during the double-blind and open-label treatment periods. The at home limit will be calculated by taking the mean of the best predose FEV1 measurements on the last 3 days before randomization on the electronic flow meter (home device) x 80%, and the investigational center limit will be the mean FEV1 of the predose pre-bronchodilator qualifying FEV1 measurements (-30 and -15 minutes) using the onsite spirometer x 80%.
- 16) A subset of patients (approximately 120 patients) at select investigational centers who successfully completed Part 1 will be eligible for enrollment into the open-label extension (Part 2).
- 17) Predose FEV1 will be measured at 30 and 15 minutes before administration of study medication. Serial FEV1 spirometry measured at 0 hours (within 30 and 15 minutes prior to study medication administration [equivalent to the predose FEV1]), and at 5 and 30 minutes postdose, and at 1, 2, 4, 6, 8, 10, 12, 23, and 24 hours postdose. The following windows are permitted: +5 minutes for predose measurements (-30 and -5 minutes) and 5 minute postdose measurement; ±5 minutes for 0.5-6 hours, and ±15 minutes for 8-24 hours.
- 18) Diary collection begins at the time of signing the ICF, and then continues throughout Part 1 and Part 2, per the randomization scheme.
- 19) Dispensation of the albuterol/salbutamol MDI is not required during the screening period if the patient is taking this medication as part of their current COPD therapy. Once the patient is enrolled in the run-in period, dispensation/administration of the study albuterol/salbutamol MDI is required and the patient will discontinue the use of their own albuterol/salbutamol MDI.
- 20) Administration of study medication at the investigational center will occur in the presence of the unblinded and blinded staff members.
- 21) For patients participating in Part 2.
- 22) Home based FEV1 measurements will not be performed on the mornings of visit 2 (both day 0 and day 1), visit 3 (both day 21 and day 22), and visit 4 (both day 42 and day 43).

